Official Title: Comprehensive Wide Bandwidth Test Battery of Auditory Function
in Veterans

NCT Number: 02019888

Document Date: 3/5/2021

Study Protocol

The goal of this research is to evaluate a comprehensive test battery of new wide-bandwidth, i.e., wideband (WB), acoustical tests of auditory function in the differential diagnosis of middle ear, cochlear and neural pathologies in a population of Veterans. WB tests refer to ear canal tests using sound responses measured from 200 Hz to frequencies as high as 8000 Hz, a bandwidth that is critical for speech perception. There will be tests in the battery for middle-ear assessment using absorbance cochlear assessment using otoacoustic emissions (OAEs) and the acoustic stapedius reflex (ASR) using middle ear power absorption. Results will be compared with a standard single-frequency clinical immittance test battery routinely used in the assessment of auditory function in Veterans.

Aim 1 seeks to evaluate the accuracy of the WB test battery in the differential diagnosis of middle-ear pathology and related conductive hearing loss by comparing the sensitivity and specificity of the WB battery to the traditional immittance battery for disorders common in Veterans including tympanic membrane perforation and serous otitis media. Aim 2 seeks to modify a WB ASR test to provide automatic detection of the ASR threshold for comparison with the traditional single-frequency ASR threshold. Aim 3 seeks to validate the use of Transient-evoked otoacoustic emission (TEOAE) and spontaneous otoacoustic emissions (SOAEs) tests in Veterans to assess cochlear status, and evaluate their test performance in classifying ears with normal hearing and sensorineural hearing loss. The combination of tests across aims will allow for examination of the diagnostic accuracy of the full WB test battery in comparison to the single-frequency admittance test battery to detect any type of hearing loss including sensorineural, conductive and mixed. The hypothesis is that the WB test battery is more accurate than the traditional immittance test battery in identifying ears with normal auditory status and ears with a range of risks for auditory pathology.

Methods:

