Subjects- Human subjects will be recruited for this study who have had a hearing evaluation from the VA Audiology Service at the Portland VA Medical Center and the H. Quillen VA Medical Center. These subjects will respond to flyers or be contacted from an IRB-approved human subject volunteer registry. Data will be acquired from three groups of subjects with normal hearing, sensorineural hearing loss (SNHL), and middle ear disorders.

Testing- All subjects will receive the same clinical and WB test battery. Each subject will be tested in one laboratory visit. Subjects will be enrolled in this study that upon otoscopic inspection of their ear canals, have no active drainage from the ears, and have ear canals free of cerumen (wax) impaction, bilaterally. Subjects who are found to have draining ears or cerumen impaction will be referred for treatment. These individuals may be enrolled in the study following successful treatment for their conditions. All subjects will have a standard pure-tone air- and bone-conduction

audiogram while comfortably seated in a sound-treated booth. Standard insert earphones and a bone-conduction vibrator will be used to present the sound stimuli. Next, speech audiometry will be completed and the speech reception thresholds, uncomfortable loudness test for speech, and speech recognition scores will be obtained. Then the subjects will have a standard immittance test battery consisting of a tympanogram and acoustic reflex threshold testing. Stimuli will not exceed a level of 100 decibels hearing level (dB HL). Finally, the wideband test battery will be performed with adults seated comfortably in a sound-treated booth. A small probe with a soft rubber tip will be inserted in the subject's ear canal, and the subject will be asked to remain quiet while sounds are presented to an ear via sound sources within the probe. Responses will be measured using a miniature microphone within the probe. The tests in the wideband battery are similar to the clinical admittance battery and include ambient absorbance, absorbance tympanometry and acoustic reflex threshold. The otoacoustic emission testing is a separate measurement of inner ear function typically conducted in the clinic using different equipment.

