## **Statistical Analysis Plan**

Analyses of variance (ANOVA) will be conducted to examine differences in outcomes measures across the three subject groups with normal hearing (NH), sensorineural hearing loss (SNHL), and middle ear disorders (ME). Bonferroni corrections will be applied for multiple comparisons. T-tests will be used to examine effects of method (clinical vs. experimental wideband) within each subject group.

For the Primary Outcome measure of Middle Ear Test, separate ANOVAs will be used to examine differences across groups within each method. In the first ANOVA, the independent variable will be subject group, and the dependent variable will be clinical tympanometric peak static acoustic admittance at 226 Hz. In the second ANOVA, the independent variable will be subject group, and the dependent variable will be wideband absorbance at ambient pressure averaged across half-octaves from 250 to 8000 Hz.

For the Secondary Outcome measure of Middle Ear Muscle Reflex Test, separate t-tests will be used to examine the difference in middle ear muscle reflex threshold between the clinical and wideband experimental methods within each subject group.

For the Secondary Outcome measure of Wideband Otoacoustic Emission Test, an ANOVA will be used to examine the differences across subject groups in transient evoked otoacoustic emission (TEOAE) signal-to-noise ratio (SNR) (averaged across half-octave bands from 1000 to 8000 Hz).

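### Aim 3 asks how well TEOAE and SOAE tests classify normal-hearing versus SNHL ears, but the SAP text available plans only a comparison of mean TEOAE SNR and no SOAE analysis

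*SAP*

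**What the plan says.** The protocol's statement of Aim 3 has two parts. It seeks to "validate the use of Transient-evoked otoacoustic emission (TEOAE) and spontaneous otoacoustic emissions (SOAEs) tests in Veterans", and to "evaluate their test performance in classifying ears with normal hearing and sensorineural hearing loss". The unit named is the ear, the contrast is normal hearing (NH) against SNHL, and the quantity sought is test performance.

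The SAP, under Statistical Analysis Plan, gives one analysis for the Wideband Otoacoustic Emission Test: "an ANOVA will be used to examine the differences across subject groups in transient evoked otoacoustic emission (TEOAE) signal-to-noise ratio (SNR"), with SNR "averaged across half-octave bands from 1000 to 8000 Hz". The opening paragraph defines the comparison as running "across the three subject groups with normal hearing (NH), sensorineural hearing loss (SNHL), and middle ear disorders (ME"), and adds that "Bonferroni corrections will be applied for multiple comparisons". It states neither the alpha level nor the number of comparisons.

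SOAE is named in Aim 3 and nowhere else in the text available. The protocol's Testing paragraph mentions emissions only generically ("The otoacoustic emission testing is a separate measurement of inner ear function") and does not say whether spontaneous emissions are recorded.

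**The concern.** An analysis of variance asks whether group means differ. A diagnostic classifier is judged by how far the two distributions overlap, and by the error rates at a cut-off. The p-value for a mean difference mixes effect size with sample size, so it cannot by itself say whether the test separates NH from SNHL ears weakly or well.

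Two things are at stake. First, an analyst following the SAP would finish without the result Aim 3 promises, for either test. Second, the gap invites a poor substitute. A significant NH–SNHL difference may be presented as validation, or cut-offs may be chosen after the data are seen, which tends to overstate accuracy.

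**Working it through.** **Comparison of the texts**

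| Element | Protocol, Aim 3 | SAP text available |
|---|---|---|
| Tests | TEOAE and SOAE | TEOAE only |
| Groups | NH and SNHL | NH, SNHL and middle ear disorders |
| Unit | Ear | Subject group; ears not mentioned |
| Quantity | Classification performance | Difference in mean SNR |
| Method | Not stated | ANOVA, Bonferroni correction |

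The SAP text contains no ROC curve, AUC, sensitivity, specificity, cut-off or classification model for any outcome. The protocol has no statistical section that supplies one. The Bonferroni sentence can reasonably be read as covering the NH–SNHL pair, but that pair is still compared on means.

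**Illustration of how far significance and classification can diverge**

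The documents give no figure to reproduce. Everything below is assumed: SNR normal with equal SD in NH and SNHL, one ear per subject, equal group sizes n, and two-sided alpha 0.05/3 (three pairwise comparisons at an overall 5%). The true difference is d standard deviations.

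1. Smallest observed difference that reaches significance: d = t(1 − 0.05/6; 2n − 2) × √(2/n). Corresponding AUC = Φ(d/√2).

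| n per group | t | Smallest significant d | AUC |
|---|---|---|---|
| 30 | 2.465 | 2.465 × √(2/30) = 0.637 | 0.674 |
| 50 | 2.436 | 2.436 × √(2/50) = 0.487 | 0.635 |
| 100 | 2.415 | 2.415 × √(2/100) = 0.341 | 0.595 |

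2. Classification at a given true difference. Sensitivity at 90% specificity = Φ(d − 1.2816). At the midpoint cut-off, sensitivity = specificity = Φ(d/2). The AUC half-width is the Hanley–McNeil 95% value at 30 per group.

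| d | AUC | Sensitivity at 90% specificity | Sensitivity = specificity at midpoint | AUC 95% half-width, n = 30 |
|---|---|---|---|---|
| 0.6 | 0.664 | 0.248 | 0.618 | 0.138 |
| 1.0 | 0.760 | 0.389 | 0.691 | 0.122 |
| 1.5 | 0.856 | 0.586 | 0.773 | 0.098 |
| 2.0 | 0.921 | 0.764 | 0.841 | 0.073 |

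3. Power of the pairwise test (noncentral t). For d = 0.6 it is 0.45 at 30 per group and 0.965 at 100 per group. At 30 per group it is 0.917 for d = 1.0 and above 0.999 for d = 1.5 and d = 2.0.

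So a test with AUC 0.66, detecting one SNHL ear in four at 90% specificity, would be declared significantly different about 97% of the time with 100 per group.

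4. Precision of sensitivity at an estimated cut-off. In 20,000 simulated trials with d = 1.0 and the cut-off set at the 10th percentile of the NH sample, the central 95% of sensitivity estimates ran from 0.17 to 0.70 at 30 per group, 0.20 to 0.64 at 50, and 0.25 to 0.56 at 100.

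**The case against.** The strongest reply is that the risk of a significant but weak classifier depends on numbers the documents do not give. With 30 per group, a true 0.6 SD difference has only 45% power, so a weak classifier would fail the test more often than not. If the real difference is near 2.0 SD, significance and good classification agree. The alpha of 0.05/3 is also an assumption, since the SAP names Bonferroni without a level or a count. All of this is correct, and it limits what the illustration shows. It does not close the gap: even with a large difference, the planned ANOVA reports no error rates and no precision for them.

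A second reply is that part of the SAP file was not in the text reviewed. The finding is limited accordingly. However, the available text does set out the analysis for the emission outcome, and it is a comparison of means.

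A third is that SOAE may be an unreconciled aim rather than a forgotten analysis, because the SAP does not list it as an outcome. That is possible. In that case the documents should say so.

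A fourth is that an ROC analysis needs an ear-level definition of NH and SNHL, which the documents do not give. This is a fair request for detail. The groups already exist in the plan and every subject has an audiogram, so it does not stand in the way of the analysis.

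**Conclusion.** The concern holds. On the SAP text available, Aim 3's stated output, classification performance of TEOAE and SOAE for NH versus SNHL ears, has no planned analysis. TEOAE gets a comparison of means; SOAE gets nothing. This conclusion rests on the wording alone and does not depend on any assumed sample or effect size.

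Its practical size cannot be fixed from the documents. Under the stated assumptions, a just-significant result implies an AUC between about 0.60 (100 per group) and 0.67 (30 per group), while a very large difference would make the two questions agree. The plan should be changed, but the point concerns a secondary outcome and the repair is simple.

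**What to change.** Add to the SAP, as the Aim 3 analysis:

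> TEOAE SNR, averaged over 1000–8000 Hz, will be evaluated as a classifier of SNHL versus NH ears by ROC analysis. The AUC with 95% CI is the main result. Sensitivity with 95% CI will also be reported at the cut-off giving 90% specificity in NH ears. Confidence intervals will come from a bootstrap that re-estimates the cut-off in each resample and resamples by subject if both ears are used.

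The 90% is an example; the investigators may fix another value before analysis. State also how an ear is assigned to NH or SNHL from the audiogram, including when a subject's two ears differ.

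For SOAE: if it is recorded, report sensitivity and specificity with 95% CIs for a criterion set before analysis, for example present versus absent. If it is not, state that this part of Aim 3 will not be assessed. If the data have already been examined, label cut-off results exploratory and rely on the AUC. Keep the ANOVA with Bonferroni comparisons as supporting analysis. If the investigators intend only a comparison of means, the alternative is to narrow Aim 3 to say so.

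The cost is SAP wording and a modest amount of analysis. TEOAE SNR is already a planned outcome, so it needs no new data; SOAE needs none only if it is recorded. The drawback is imprecision: with small groups, sensitivity at a fixed specificity is poorly estimated, which is why the AUC should lead.

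### TEOAE SNR is tested only as one average across bands: a loss in part of the range can be missed, and no analysis answers Aim 3's classification question

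*SAP*

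**What the plan says.** The SAP's paragraph on the Wideband Otoacoustic Emission Test, a secondary outcome, defines the variable as TEOAE SNR "averaged across half-octave bands from 1000 to 8000 Hz". It applies one ANOVA, with subject group (normal hearing, NH; sensorineural hearing loss, SNHL; middle ear disorder) as the only factor. On multiplicity the SAP says only that "Bonferroni corrections will be applied for multiple comparisons", without an alpha or a count of comparisons.

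The protocol's Aim 3 is to "validate the use of Transient-evoked otoacoustic emission (TEOAE) and spontaneous otoacoustic emissions (SOAEs) tests in Veterans to assess cochlear status", and to "evaluate their test performance in classifying ears with normal hearing and sensorineural hearing loss".

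The supplied text has no band-level TEOAE analysis, no group-by-band term, and no ROC, sensitivity or specificity analysis of TEOAE. The number of half-octave bands is not stated.

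**The concern.** An average over bands gives every band equal weight. When hearing loss is confined to part of the range, the unaffected bands pull the group difference towards zero and still contribute their own variability. A real deficit in two or three bands could give a non-significant ANOVA. Even a significant result would not say which frequencies separate the groups. Band values must exist before they can be averaged, so the information is already collected.

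There is also a gap against Aim 3. A comparison of group means does not measure how well individual ears are classified as NH or SNHL. At stake is a secondary outcome that could understate what TEOAEs can detect and leave the aim's own question unanswered.

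**Working it through.** **Inputs.** From the SAP: half-octave bands, 1000 to 8000 Hz, one mean, one ANOVA. The documents state no power figure to reproduce, and no sample size, SD, effect size or band correlation. Everything below is therefore assumed: equal SD in each band, common correlation ρ of 0.2 or 0.5, n = 30 per group, and an NH-versus-SNHL contrast.

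**Number of bands.** Centres at 1000 × 2^(i/2) Hz are 1000, 1414, 2000, 2828, 4000, 5657 and 8000, so K = 7 if the limits are band centres. K = 6 if they are outer edges.

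**Dilution.** For a loss of d SD in k of K bands:
- shift of the mean = (k/K) × d
- SD of the mean = √[(1 + (K − 1)ρ)/K]
- standardised effect = shift ÷ SD

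For K = 7, k = 2, d = 0.8, ρ = 0.5: the shift is 2/7 × 0.8 = 0.229, the SD is √(4/7) = 0.756, and the effect is 0.30.
For K = 7, k = 3, d = 1.0, ρ = 0.2: the shift is 3/7 = 0.429, the SD is √(2.2/7) = 0.561, and the effect is 0.76.
These are the extremes over k = 2 or 3 and d = 0.8 to 1.0.

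**Power.** For the average: two-sided t-test at 0.05, 58 df, noncentrality = effect × √(n/2). For group by band: two-group Hotelling profile test at the stricter level of 0.025, with 6 and 53 df and noncentrality (n/2) × d² × k(1 − k/K)/(1 − ρ). For k = 2, d = 0.8, ρ = 0.5 this is 15 × 0.64 × 1.429/0.5 = 27.4.

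| Loss per band | ρ | Bands affected (of 7) | Average | Group by band |
|---|---|---|---|---|
| 0.8 SD | 0.2 | 2 | 34% | 77% |
| 0.8 SD | 0.2 | 3 | 64% | 86% |
| 0.8 SD | 0.5 | 2 | 21% | 95% |
| 0.8 SD | 0.5 | 3 | 41% | 98% |
| 0.5 SD | 0.2 | 3 | 31% | 36% |
| 0.5 SD | 0.2 | 4 | 49% | 36% |
| 0.5 SD | 0.2 | 5 | 68% | 29% |
| 0.5 SD | 0.2 | 6 | 83% | 16% |
| 0.5 SD | 0.5 | 5 | 44% | 50% |
| 0.5 SD | 0.5 | 6 | 58% | 28% |

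With six bands, the 0.8 SD cases give 26% to 75% for the average and 77% to 97% for group by band, so the band count does not drive the result.

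**Uniform loss.** If all seven bands lose 0.5 SD, there is no interaction to find. The average has 92% power (ρ = 0.2) or 71% (ρ = 0.5). Testing it at 0.025 to make room for a second test lowers these to 87% and 60%.

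**Classification.** Under normality, AUC = Φ(effect/√2). Effects of 0.30 to 0.76 give AUC 0.58 to 0.71 for the averaged score. The best linear combination of the same bands has population AUC 0.79 to 0.91; a classifier estimated from data would do somewhat worse. The plan contains neither classifier.

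**Covariance.** A mixed model with only a random subject effect assumes equal correlation between all bands. In three-group simulations with 30 per group, no true interaction, and correlation decaying with band distance (adjacent bands 0.5 to 0.9), its interaction test at nominal 2.5% rejected about 4% to 8% of the time.

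**The case against.** The average is a clear, prespecified summary of a secondary outcome. It reduces noise, needs one test and no alpha split, and wins when the loss is broad, or when it is modest, covers about half the bands or more, and band correlation is low. The documents do not describe the SNHL group's audiometric pattern, so nobody can say from them which situation applies. The tabulated group-by-band power is for two groups; with three groups and seven bands the term has 2 × 6 = 12 df, so the figures are indicative only. All of this stands. It is why the average should be kept and not replaced.

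Three stronger readings are tempting, and the documents do not support them:
- **That Aim 3 requires frequency-specific results.** The protocol defines wideband testing by "sound responses measured from 200 Hz to frequencies as high as 8000 Hz, a bandwidth that is critical for speech perception", but it states no frequency-specific objective. Aim 3 is set at ear level, and one score per ear can serve it, though perhaps less well.
- **That averaging is simply the inferior test.** The table shows the direction changing with the size and extent of the loss and with band correlation.
- **That the plan will understate TEOAE classification accuracy.** No classifier is planned. The AUC figures show only what one built on the average might do if the loss covers part of the range.

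Nor does the SAP rule out later band-level reporting. It leaves such reporting unplanned, and therefore open to selection after the data are seen.

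**Conclusion.** The point holds in conditional form. A loss in k of K bands shifts the averaged SNR by only k/K of the per-band loss. For 0.8 SD in two or three of seven bands, the assumed inputs put the average 22 to 74 percentage points behind a group-by-band test (86 − 64 and 95 − 21). For broad loss the order reverses. The planned ANOVA cannot locate a difference under any pattern.

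The mismatch with Aim 3 needs no assumed numbers: the aim asks for classification performance, and the supplied text analyses only group means. Because the outcome is secondary and the size of the power loss rests on assumed effects, correlations and n, this is a worthwhile addition to the plan. It does not invalidate the planned test.

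**What to change.** 1. Keep the averaged-SNR ANOVA as planned, at its full alpha. Splitting alpha would cost 5 to 11 points of power under uniform loss (92 − 87 and 71 − 60).
2. State the number of bands, and whether 1000 and 8000 Hz are centres or edges.
3. Prespecify a supporting model of band SNR with group, band and group by band, using an unstructured or otherwise justified band covariance, or a multivariate profile test. A random subject effect alone is not enough. Report Holm-adjusted group contrasts within bands.
4. For Aim 3, prespecify a cross-validated NH-versus-SNHL ROC built from the band SNRs, reported beside the ROC of the averaged SNR.

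The cost is SAP wording and extra analysis of data already collected. The band-level result would be supporting, not confirmatory, and should be labelled so.
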